RESEARCH PROTOCOL

Continuous Glucose Monitoring for Hyperglycemia in Critically Ill Patients

NCT05442853

October 20, 2022

RESEARCH PROTOCOL

1. **Project Title:** Continuous Glucose Monitoring for Hyperglycemia in Critically III Patients

2. Abstract:

The investigators intend to conduct prospective, randomized comparative trial of patients admitted to the intensive care unit (ICU) at the North Florida/South Georgia Veterans Health System who received continuous glucose monitoring (CGM) vs standard glucose monitoring. This study will examine several outcomes for patients in the ICU with hyperglycemia. The primary outcome of the study will be the percentage of time in target range (blood glucose 70-180 mg/dL). Secondary outcomes will include percentage of time in clinically significant hypoglycemic (BG < 54 mg/dL), hypoglycemic (BG 54-69 mg/dL), hyperglycemic (BG 181-250 mg/dL), and clinically relevant hyperglycemic (BG >250 mg/dL) ranges; ICU length of stay, ICU mortality, 30-day mortality, costs associated with monitoring, mean BG, glucose variability between the two groups (% coefficient of variation = SD/mean BG*100%), and patient satisfaction. An evaluation will be done to assess the proportions of patients with new infection, acute kidney injury (AKI), agitation, delirium, and pain. Correlation between CGM values and whole blood values for blood glucose will be evaluated.

3. Background:

Diabetes mellitus (DM) is a common comorbidity among hospitalized patients with over 25% reporting a history of the disease. Furthermore, stress-induced hyperglycemia is common in critically ill patients. Among these patients, glucose control is a necessity to avoid further complications. Inpatient hyperglycemia has been associated with a longer length of stay, increased risk of infection, and increased mortality. Hypoglycemia can be more severe in hospitalized patients and can also increase length of stay and mortality. The current standard for glucose monitoring involves point-of-care (POC) blood glucose finger sticks or arterial/venous whole blood sampling. These methods have limitations and continuous glucose monitors (CGMs) offer a potential alternative.

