Continuous glucose monitors (CGMs) were originally designed for use in the home and outpatient setting, with less data on its application in the hospital or critical care settings. Until April 2020, CGMs were not approved for inpatient use. To support COVID-19 healthcare efforts, the FDA allowed for the use of continuous glucose monitoring (CGM) systems for the treatment of patients in various healthcare facilities. This remote glucose monitoring allowed for conservation of personal protective equipment (PPE) and reduction of potential exposure of staff from multiple point-of-care glucose checks. Compared to the POC checks every one to two hours, CGM systems can provide blood glucose readings multiple times each hour, allowing for remote monitoring and the ability to detect urgent changes in blood glucose.

Several studies have evaluated the use of CGM among hospitalized patients with DM and have shown positive results when compared to traditional POC glucose

monitoring. Most studies have found the use of CGM can help minimize the number of hypoglycemia episodes and overall improve patient care. Similar studies have been done in the intensive care unit (ICU) with favorable results; however, these studies had smaller sample sizes and limited external validity. While there is consensus on the superiority of CGM detecting hypoglycemic blood glucose levels, the effects on other patient outcomes in the critically ill remain uncertain.

4. Study Purpose:

The purpose of this study is to compare the use of CGM versus POC glucose monitoring in the critical care setting for differences in glycemic control and other important ICU outcomes.

5. Research Plan:

a. Study Design:

i. Prospective, single-center, randomized comparative trial

b. Study Sample:

- Adult patients at North Florida/South Georgia Veterans Health System anticipated to be admitted to an ICU for a minimum of 48 hours after enrollment
- A minimum sample size was calculated to be a total of 88 patients (44 per group), but will continue to enroll patients for a maximum of 2 years or a maximum of 300 patients
 - 1. Anticipated mean POC % time in range of 58% (based on current rates in our facility) with a standard deviation of 20%
 - 2. Anticipated mean CGM % time in range of 70% (based on CGM interpretation guidelines)
 - 3. 80% power, 5% alpha

c. Inclusion Criteria:

- i. Patients age 18-89

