- Past medical history of any diabetes mellitus OR patients with at least 1 measured BG of 180 being treated with insulin (subcutaneous or infusion)
 - 1. Enrollment will occur within 72 hours after being admitted to an ICU if history of diabetes
 - 2. Enrollment will occur within 72 hours after developing hyperglycemia in ICU if no diabetes

d. Exclusion Criteria:

- i. Pregnant patients
 - Female patients who report no known current pregnancy, will be considered to not have potential to be pregnant with one of the following:

- a. History of surgical sterilization (methods include hysterectomy, bilateral tubal ligation, bilateral salpingectomy or bilateral oophorectomy)
- b. Postmenopausal (defined as age greater than 62 years, or age 62 years or less than with amenorrhea for at least 12 consecutive months)
- c. No sexual partners within previous 9 months who can father children (those who cannot father children include female partners; and male partners who are incapable of fathering children because of congenital anomalies, surgery, or medical treatment)
- d. Reported consistent use of hormonal (oral contraceptives, implant, injection, patch, vaginal ring) or intrauterine device (IUD) contraception.
- ii. Diagnosis of diabetic ketoacidosis (DKA)
- iii. Diagnosis of hyperosmolar hyperglycemic state (HHS)
- iv. Anticipated to require prone positioning while on insulin therapy
- v. Any contraindications to CGMs based on manufacturer labeling
- vi. BG above maximum reading for CGM (e.g. greater than 400 mg/dL)
- vii. Receiving medication that could interfere with CGM readings (based on manufacturer specifications)
 - 1. Receiving any dose of hydroxyurea as this could falsely elevate the sensor readings (if applicable for specific CGM)
 - Receiving greater than 1,000mg acetaminophen every 6 hours in any form as this could falsely elevate the sensor readings (if applicable for specific CGM)

e. Recruitment:

- Patients who meet eligibility criteria for this study may be referred to the study team by a clinical staff member of the ICU team responsible for the clinical care of the patient. Study team members are ICU clinicians and may also be part of the team providing clinical care.
 Patients (or their authorized decision maker) will first be asked if they wish to learn about the study. If the patient is interested in participating in the study, the research team will contact the patient and provide details of study participation and informed consent.

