- ii. Patients will be provided information on standards of care. As a participant in this study, all care including medical procedures, diagnostic tests, monitoring, medications, treatments, and other care will be the same for all patients as those who do not participate in the study, with the exception of the method of glucose monitoring.

f. Randomization:

- i. Study participants will be randomly assigned to one of the study groups after being found eligible for inclusion and giving consent to participate
- ii. A randomization process, such as a computerized algorithm or random number generator will be used to assign patients a group upon inclusion
- iii. Patients will be allocated 1:1 to the monitoring groups based on this randomization

g. Study Groups:

- i. Group 1: POC group (Blinded to CGM)
 - 1. All patients will have Dexcom G6 Pro CGM sensor/transmitter placed per device instructions
 - 2. Nurses and all members of the medical treatment team will be BLINDED to the CGM blood glucose readings during the study period
 - 3. Glycemic management will be based on POC glucose values.
- ii. Group 2: CGM group (Unblinded to CGM)
 - 1. All patients will have Dexcom G6 CGM sensor/transmitter placed per device instructions
 - 2. Nurses and all members of the medical treatment team will be UNBLINDED to the CGM blood glucose readings during the study period
 - 3. Glycemic management will be based on CGM values.

h. Study Outcomes

i. Primary Outcome

- Percentage of time in target range (BG 70-180mg/dL) [Appendix E]
 - a. Comparison of CGM readings between both types of monitoring/treatment groups

ii. Secondary Outcomes

- Percentage of time in each range (Appendix E) [Comparison of CGM readings between both types of monitoring/treatment groups]
 - a. Clinically significant hypoglycemic range (BG < 54 mg/dL)
 - b. Hypoglycemic range (BG 54-69 mg/dL)
 - c. Hyperglycemic range (BG 181-250 mg/dL)
 - Clinically relevant hyperglycemic range (BG >250 mg/dL)
- 2. ICU length of stay
- 3. ICU mortality
- 4. 30-day mortality

- 5. Costs associated with monitoring
- 6. Mean BG
- 7. Glucose variability for each group
 - a. % coefficient of variation = SD/mean BG*100%
- 8. Patient satisfaction

iii. Safety

- 1. Proportion of patients with a new infection
- 2. Proportion of patients with new AKI (AKIN guidelines)
- 3. Proportion of patients with CAM-ICU positive delirium
- 4. Proportion of patients with agitation (RASS \geq 2)

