- 5. Proportion of patients with a positive pain score (CPOT vs DVPRS)
 - a. Correlate pain score with timing of BG check for POC and at time of placement of CGM

i. Inpatient Hyperglycemia Management:

- i. Hyperglycemia management will be directed by the ICU team per standard of care
- ii. Standard nutritional guidelines are recommended. Nutritional care will be managed at the discretion of the providers
- iii. IV insulin infusion targeting BG 140-180 mg/dL is preferred treatment, especially if NPO, on an inconsistent nutritional regimen, hemodynamically unstable, or in setting of organ dysfunction
 - Will use validated protocol with computerized decision support tool (Appendix D)
 - 2. Converting from IV insulin infusion to SC insulin managed as described in Appendix D
- SC insulin regimen may be used based on the discretion of the treating ICU team, with dosing/agents recommended in Appendices A, B, and C
 - 1. Only recommended for patients on consistent nutritional regimen who are hemodynamically stable
 - Daily insulin dose adjustments to the SC insulin regimen will be managed at the discretion of the treating ICU team, considering use of correctional insulin and concomitant factors (e.g. use of medications which increase blood glucose)

j. Hypoglycemia Management:

- i. Managed per protocol in both groups.
 - 1. If able to eat/swallow, 15 grams of carbohydrates (glucose tablets/glucose gel) PRN
 - 2. If unable to eat/swallow or developed severe hypoglycemia, ½ ampule vs 1 ampule intravenous D50W PRN

- 3. If no intravenous access is available, 1mg glucagon subcutaneous PRN
- ii. Additional treatment may be given after 15 minutes if the patient has an inadequate response to the glucose correction.

k. CGM Devices:

- Two CGM devices will be used in this study, Dexcom G6 and Dexcom G6 Pro. Both devices are placed similarly onto patients. Both devices can be worn for same timeframe (10 days). Both devices can interact with same applications, smartphone, and manufacturer software (Dexcom Clarity). Both devices carry same manufacturer instructions for placement and use with specific medications and diagnostic procedures. Dexcom G6 can only be used in an Unblinded mode where CGM values are visible to the patient and clinical care team. Dexcom G6 Pro allows for a Blinded mode where CGM values are not visible to patients or the clinical care team.
- ii. Dexcom G6
 - 1. Will be used in the CGM group
 - 2. Used only in Unblinded mode

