 - 3. Sensor and transmitter are separate components
- iii. Dexcom G6 Pro
 - 1. Will be used in the POC group
 - 2. Will be used in Blinded mode
 - 3. Sensor and transmitter are combination device

I. Blood Glucose Correlation:

- i. CGMs will be calibrated if necessary, per manufacturer instructions with POC or venipuncture BG sample
- ii. CGM and POC tests will be correlated with routine venipuncture monitoring on at recommended daily interval unless clinical suspicion of an inaccurate reading

m. POC Group Procedures:

- i. CGMs will be placed on the abdomen (or other site) per manufacturer recommendations and can be at the discretion of placing provider.
 - a. Placement at least 3 inches from insulin pump infusion or injection site
 - b. Placement away from waistband, scarring, tattoos, irritation, and bones
 - c. Placement in a location unlikely to be bumped, pushed, or laid on while sleeping
 - d. CGMs will be removed prior to any surgery, computed tomography (CT) scan, or magnetic resonance imaging

(MRI), or other procedure as necessary per manufacturer instructions

- ii. Patients, nurses, and other treatment team will be blinded to the CGM readings
 - 1. All treatment decisions for this group will be based on POC readings and venipuncture
- iii. POC BG will be checked per protocol based on treatment received
 - 1. Every 1-2 hours per protocol if receiving an insulin infusion
 - 2. At least 3 times per day if receiving a basal:bolus insulin regimen

n. CGM Group Procedures:

- i. CGMs will be placed on the abdomen (or other site) per manufacturer recommendations and can be at the discretion of placing provider.
 - a. Placement at least 3 inches from insulin pump infusion or injection site
 - b. Placement away from waistband, scarring, tattoos, irritation, and bones
 - c. Placement in a location unlikely to be bumped, pushed, or laid on while sleeping
 - 2. Remote monitoring software will be set up for nursing staff
 - 3. All staff will be educated on using the monitoring software
 - CGMs will be removed prior to any surgery, computed tomography (CT) scan, or magnetic resonance imaging (MRI), or other procedure as necessary per manufacturer instructions
- ii. Nurses and treatment team will NOT be blinded to the CGM readings
 - 1. All treatment decisions for this group will be based on CGM readings, confirmatory POC readings (as necessary), and venipuncture

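### The only accuracy analysis named for the sensor that scores the primary endpoint is a correlation, not split by arm, which barely registers a proportional bias

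*Combined protocol and SAP*

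**What the plan says.** All references are to the combined protocol and SAP.

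- **Endpoint (5.h.i).** The primary outcome is defined as "Comparison of CGM readings between both types of monitoring/treatment groups". No blood-based version is named.
- **Arms (5.g).** In the POC group, "All patients will have Dexcom G6 Pro CGM sensor/transmitter placed per device instructions"; staff are blinded to it and treat on POC values. The CGM group wears the G6, staff see it, and "Glycemic management will be based on CGM values".
- **Devices (5.k).** Placement and wear time are alike, and "Both devices carry same manufacturer instructions for placement and use with specific medications and diagnostic procedures". Nothing is said about accuracy.
- **Operational checks.** Section 5.l.i provides for calibration when needed, following the manufacturer. Section 5.n adds, for the CGM group, a confirmatory POC test for hypoglycemia alarms and for readings below 40 mg/dL, with venipuncture if the two disagree. Section 5.m has no counterpart for the POC group.
- **Accuracy analysis.** Section 5.l.ii states: "CGM and POC tests will be correlated with routine venipuncture monitoring on at recommended daily interval unless clinical suspicion of an inaccurate reading". The abstract states: "Correlation between CGM values and whole blood values for blood glucose will be evaluated". Neither mentions mean bias, limits of agreement or a split by arm, and section 6 names no specific method.
- **Sensor error acknowledged.** Section 7 lists inaccurate glucose measurement as a risk, and 5.d.vii excludes drugs that could falsely raise readings.
- **Design figures (5.b).** "Anticipated mean POC % time in range of 58% (based on current rates in our facility) with a standard deviation of 20" percent; 70% expected with CGM; 80% power and 5% alpha; at least 44 per arm, at most 300 patients in all.

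**The concern.** Putting a sensor on every patient is sound: it avoids comparing a continuous trace with intermittent finger sticks. It also means that any difference in mean sensor error between the arms enters the primary result directly. Randomization balances the patients but not the instruments, because device model, visibility and confirmatory checks are all assigned with the arm. The protocol does not say how, or by whom, a blinded sensor would be calibrated, or that calibration practice must match.

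A correlation measures how tightly two readings move together, not whether one sits above the other. It could therefore look good in a trial where one arm's sensors read several percent high or low. The observed difference would then mix glucose control with sensor error, in either direction. Enrolling toward 300 would not dilute this error; it would make it more likely to reach significance.

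**Working it through.** **1. The plan's sample size.** n per arm = 2(1.960 + 0.842)² × 20² / 12² = 43.6, so 44 per arm and 88 in total. This reproduces.

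**2. Model.** The documents give no sensor-error figure and no within-patient glucose spread, so both are assumed. True glucose is the same in both arms. Each patient has a mean m and within-patient SD s, and the between-patient mean and SD are solved so that average time in range is 58% and its patient SD is 20%. For s = 30 mg/dL this gives m with mean 173.3 and SD 17.9.

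**3. What r does.** Let the sensor read y = x(1 + o + B + E), with offset o, patient bias B (SD 10%) and pair noise E (SD 10%). Then

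r = 1 / √[1 + 0.02 · E(x²) / ((1 + o)² · Var x)].

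At s = 30, Var x = 30² + 17.9² = 1220 and E(x²) = 173.3² + 1220 = 31,253, so the second term is 0.512/(1 + o)².

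| Offset | r | Mean relative bias |
|---|---|---|
| -10% | 0.783 | -10% |
| -5% | 0.799 | -5% |
| 0 | 0.813 | 0 |
| +5% | 0.826 | +5% |
| +10% | 0.838 | +10% |

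The largest movement is about 0.03. By the same formula it is 0.035 at s = 25 (mean 174.6, SD 14.8) and about 0.02 at s = 40 (mean 168.0, SD 27.7). If the errors multiply instead of adding, r does not move at all. With no offset, r already runs from 0.757 (s = 25) to 0.891 (s = 40), so glucose spread affects it far more than bias does.

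**4. What the endpoint does.** For a sensor reading b times the truth, a patient's time in range is Φ((180.5/b − m)/s) − Φ((69.5/b − m)/s). Averaging over patients at s = 30 gives a total SD of √(30² + 17.9²) = 34.93:

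- b = 1: Φ(0.206) − Φ(−2.972) = 58.0%
- b = 0.95: Φ(0.478) − Φ(−2.867) = 68.2%, a shift of 10.1 points before rounding.

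Across the grid, a -5% offset in one arm gives:

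- normal, s = 25, 30, 35, 40, 45: 12.2, 10.1, 8.5, 6.9, 4.4 points
- lognormal, CV 15, 20, 25, 30, 35%: 11.1, 8.5, 6.8, 5.4, 4.1 points; with normally distributed patient means the last two become 5.2 and 3.5.

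A +5% offset gives shifts of similar size in the other direction. The range is therefore about 3.5 to 12 points.

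**5. Chance of a false positive, no true effect.** SE = 20√(2/n), which is 4.26 at 44 per arm and 2.31 at 150. A shift of 4.1 points is significant in 16% of trials at 44 per arm and 43% at 150; a shift of 12.2 points in 82% and over 99%. At 3.5 points the figures are 13% and 33%.

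**6. Precision of a by-arm bias check.** SE = √(10² + noise²/k) · √(2/n), with k pairs per patient.

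- n = 44, noise 10%, k = 10: √110 × 0.2132 = 2.24, CI ±4.4 percentage points
- n = 44, noise 15%, k = 2: √212.5 × 0.2132 = 3.11, CI ±6.1 percentage points

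Power at 44 per arm is 36-61% for a 5% difference in bias and 90-99% for 10%. At 150 per arm the CI is ±2.4 to 3.3, with 84-99% power for 5%.

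**7. Precision of the venipuncture proportion.** The mean of p(1 − p) is 0.58 × 0.42 − 0.20² = 0.2036. Patient-level variance is 400 + 2036/k in squared points: SD 37.7 at k = 2 and 24.6 at k = 10. The CI is then about ±10 to 16 points at 44 per arm and ±6 to 9 at 150.

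**The case against.** Much of the other side's case stands.

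- **It is not the only check.** A reader might infer that accuracy is otherwise unguarded. It is not: calibration and the CGM-arm confirmatory samples exist. They are care procedures rather than analyses, though. The confirmatory samples address low readings, while most of the shift computed above arises at the 180 mg/dL boundary.
- **No coefficient is named.** The clause in 5.l.ii can be read as a daily cross-check, and section 6 leaves methods open. That is fair, but the abstract does list correlation as an evaluation, and nothing commits the team to bias or to a split by arm.
- **No arm-specific bias is shown.** A reader might infer that the two models err differently, or that the primary result will be biased. The documents support neither. Section 5.k points toward similarity, and a different model does not imply a different mean bias. The shifts in steps 4 and 5 need a mean offset confined to one arm, and its likelihood cannot be judged from the documents.
- **Being steered by the scoring sensor is a small problem by itself.** A reader might infer that sensor-guided treatment alone invalidates the comparison. With mean-zero sensor error, modeled effects ran from 0.04 to 3.9 points with a median of about 1.0; these figures were not rechecked. A 1-point shift gives 5.6% rejection at 44 per arm, against 5% nominal.
- **The pairs will exist anyway,** so bias by arm could be computed later. That is true of the analysis. It is not true of matched, logged calibration, which must be in place during enrollment.

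**Conclusion.** The point holds as a gap in the plan, not as evidence of bias. The endpoint is scored only by sensor, under conditions that differ by arm, and the one accuracy analysis named is nearly insensitive to the error that would matter most. Should mean bias differ by 5% between arms, the measured difference would move by about 3.5 to 12 points against a planned 12, and no named analysis would show it. These sizes rest on assumed glucose spread, distribution shape and sensor error, fitted to the plan's 58% and 20%. The remedy is a cheap, worthwhile improvement; the primary test and the sample size stay as they are.

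**What to change.** 1. In 5.l.ii, alongside the correlation, report mean sensor-minus-venipuncture bias (in %) by arm and the arm difference, each with a 95% CI. Use routine daily pairs that were not used for calibration and were not triggered by an alarm, a discordant reading or suspicion of error.
2. Apply the manufacturer's calibration instructions by the same rule in both arms, as far as blinding allows, and log every calibration by arm.
3. Pre-specify, as a supportive sensitivity analysis, the per-patient proportion of routine venipuncture values within 70-180 mg/dL, compared between arms with a 95% CI.
4. Optional: time in range after rescaling each trace by that patient's mean sensor/venipuncture ratio. It relies on few noisy pairs and does not remove a slope error.

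**Cost.** Protocol wording, a calibration log, time-matching of pairs, flags on triggered draws, and programming; item 4 also needs export of the traces. No extra blood draws are needed. The drawback is low precision at 44 per arm (steps 6 and 7), and routine draws represent only their own times of day. The results would qualify the conclusion; a null finding would not exclude bias.

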- ii. The principal investigator has the responsibility for security of the study
- iii. Study data will be entered, managed, and stored securely using VA Research Electronic Data Capture (REDCap).
- iv. Study data will be coded then de-identified for data analysis.

6. Analysis Methods:

Descriptive statistics and inferential statistical methods will be used as appropriate to report findings of this study.

To minimize risk of bias, data collection and analysis will be by performed by study team members not involved in the clinical care of the study participants, as possible.

7. Possible Discomforts and Risks:

- Inaccurate measurement of BG which could lead to hypo- and hyperglycemia
- CGMs are minimally invasive but could cause some patients mild physical pain or discomfort
- Apart from the type of monitoring utilized, no further changes to patient care will be made. Investigators will not alter medication prescribing to deviate from standard of care. As such, no additional discomfort or risk to the patient caused by this study is expected.

8. Possible Benefits:

- Reduction of serious hypoglycemia or other adverse events is the most relevant potential benefit of using CGM
- Decreased point-of-care finger sticks compared to standard care. This may lead to benefits such as increased patient comfort and reduced costs.
- Possible benefit of improved glycemic control with the ability to monitor glucose levels more carefully and adjust treatment as appropriate; this could lead to improved patient outcomes. We hypothesize the use of CGM will yield less cases of hypoglycemia and more glucose values at goal.

9. Anticipated Costs:

GGM devices and other necessary equipment will be provided through a manufacturer sponsored grant. Administrative and regulatory expenses will be covered by a manufacturer sponsored grant. No other costs beyond investigator salary and those for routine clinical care are anticipated.

10. Conflicts of Interest:

None of the investigators hold a patent or license for any material, object, or process involved with this research. None of the investigators own stock in or serve as consultants to any company involved in this research. The researchers will not receive payment or other financial incentive for conducting this study.

The PI or any of the Sub-investigators have no real or potential conflict of interest with regards to this research project.

11. References:

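### Section 6 names no primary model; a prespecified covariate-adjusted comparison of time in range may be more precise than the unadjusted one implied by the sizing, at small cost

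*Combined protocol and SAP*

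**What the plan says.** Section 5.b sets the minimum at 88 patients, 44 per group, and adds that the trial "will continue to enroll patients for a maximum of 2 years or a maximum of 300 patients". The inputs are "Anticipated mean POC % time in range of 58% (based on current rates in our facility) with a standard deviation of 20" percent, 70% under CGM, 80% power and 5% alpha. No covariate or R² term appears.

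Section 5.h.i describes the primary outcome only as "Comparison of CGM readings between both types of monitoring/treatment groups". Section 5.f describes 1:1 randomisation and names no stratification factor. Section 6 adds: "Descriptive statistics and inferential statistical methods will be used as appropriate to report findings of this study". Adjustment is neither planned nor excluded anywhere.

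Patients differ at entry by design. Under section 5.c a history of diabetes qualifies on its own; without one, a glucose of 180 under insulin treatment is needed. Section 5.i says "IV insulin infusion targeting BG 140-180 mg/dL is preferred treatment", but also leaves subcutaneous insulin open to the treating team. On timing, section 5.c states: "Enrollment will occur within 72 hours after being admitted to an ICU if history of diabetes". For patients without diabetes the 72 hours run from the onset of hyperglycaemia in the ICU. Section 5.o already lists comorbidities, blood glucose and antidiabetic treatments for extraction from the patient record.

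**The concern.** Information that may predict time in range exists before randomisation and is already due to be extracted, yet no analysis is planned to use it. An unadjusted randomised comparison is unbiased, and its standard error already allows for chance imbalance, so validity is not at stake. Two other things are:

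- **Precision.** If the baseline variables predict the outcome even modestly, adjustment narrows the interval at the same sample size.
- **Prespecification.** With the method left open, both the decision to adjust and the choice of covariates could be made after results are known.

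Section 6 has to name a primary method in any case, and naming an adjusted one adds little work.

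**Working it through.** **Inputs.** From section 5.b: difference 70 − 58 = 12 points, SD 20, alpha 5%, power 80%, minimum N = 88, cap 300. From section 5.f: 1:1 allocation. Assumed: R² from 0 to 0.3, because the documents give no value.

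**Reproducing the plan's figure.** n per group = 2 × (1.96 + 0.8416)² × (20/12)² = 43.6, so 44 per group and 88 in total, an exact match. A one-sided 5% test gives 35 per group (70 in total), which does not match. The two-sided test is therefore inferred; the protocol does not state it.

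**Unadjusted comparison at 88.** SE = 20 × √(2/44) = 4.264. With 86 degrees of freedom the critical t is 1.988, so the half-width is 1.988 × 4.264 = 8.48 points. Noncentral-t power for 12 points is 79.5%.

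**Adjusted comparison, three covariate terms.** SE = 20 × √[(1 − R²) × (2/n) × (N − 3)/(N − 6)], with N − 5 degrees of freedom. The factor (N − 3)/(N − 6) is the price of estimating three coefficients. For N = 88 and R² = 0.2: SE = 4.264 × √(0.8 × 85/82) = 3.883, half-width 1.989 × 3.883 = 7.72, power 86.3%.

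**Break-even.** Setting (1 − R²) × 85/82 = 1 gives R² = 3/85 = 0.035; the slightly larger critical t makes it 0.036.

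Power for 12 points (%) and, in brackets, 95% CI half-width in points:

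| N | Unadjusted | R² = 0 | R² = 0.1 | R² = 0.2 | R² = 0.3 | Break-even R² |
|---|---|---|---|---|---|---|
| 88 | 79.5 (8.48) | 78.0 (8.63) | 82.1 (8.19) | 86.3 (7.72) | 90.4 (7.22) | 0.036 |
| 120 | 90.3 (7.23) | 89.6 (7.33) | 92.4 (6.95) | 94.9 (6.55) | 97.0 (6.13) | 0.026 |
| 150 | 95.5 (6.45) | 95.1 (6.52) | 96.8 (6.19) | 98.1 (5.83) | 99.1 (5.46) | 0.021 |
| 200 | 98.8 (5.58) | 98.7 (5.62) | 99.3 (5.33) | 99.7 (5.03) | 99.9 (4.70) | 0.015 |
| 300 | 99.9 (4.54) | 99.9 (4.57) | >99.9 (4.33) | >99.9 (4.09) | >99.9 (3.82) | 0.010 |

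To match adjusted power at 88 patients, an unadjusted analysis would need about 94, 106 or 120 patients at R² = 0.1, 0.2 or 0.3.

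**Simulation of the proposed model with HC2 standard errors** (44 per group, 100,000 trials per setting; assumed 70% with diabetes, infusion in 50% of those with diabetes and 60% of those without). Power was 78.2, 82.1, 86.2 and 90.5% at R² = 0, 0.1, 0.2 and 0.3, with type I error 5.0–5.2%. With an outcome bounded at 0–100 (beta distribution, 20,000 trials), adjusted power was 77.6, 81.7, 85.3 and 89.8% against 78.6–79.2% unadjusted, with type I error 4.9–5.1%.

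**Sparse covariate levels.** The chance that a level holds fewer than 5 of 88 patients is 5.3%, 54.9% or 96.8% if its true share is 10%, 5% or 2%. In simulations with one or both binary covariates at 95% in one level (40,000 trials, R² = 0.1), a rule dropping such covariates was triggered in 55–80% of trials. Power stayed at 81.6–81.9% and type I error at 5.0–5.3%.

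**The case against.** The strongest case against is that nothing is wrong and the benefit rests on an unknown number. The documents give no R², and several features point to a low one:

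- a common infusion target of 140–180 mg/dL;
- up to 10 days of CGM wear set against covariates measured once;
- no baseline CGM period;
- entry criteria that restrict glucose, because patients without diabetes need a value of 180 on insulin and values above the CGM maximum are excluded.

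At R² = 0.05 the gain at 88 patients is trivial: power 80.0% against 79.5%, half-width 8.42 against 8.48. Since 88 is only a floor, power may be ample without adjustment. A two-sample t-test would fill the gap in section 6 equally well, and sizing on the unadjusted SD is a common conservative choice that does not preclude later adjustment. The proposed model also brings an averaging window, an imputation rule and a covariate-dropping rule. A single covariate would cost less (79.0% power at R² = 0).

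Most of this stands. Nothing in the documents makes R² of 0.2–0.3 more likely than 0–0.05, and an unadjusted primary analysis is defensible if section 6 says so in advance. These points limit the expected gain, but they do not make the adjusted model unsound: its loss is bounded at about 1.5 points of power, its rules do not look at outcomes, and its data come from records already listed for extraction.

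**Conclusion.** The point holds as a low-cost improvement. The sizing reproduces only as an unadjusted two-sided comparison, section 6 leaves the method open, and prespecified adjustment may gain precision. At 88 patients the effect on power runs from a loss of 1.5 points (R² = 0) to a gain of 10.9 points (R² = 0.3, 90.4 − 79.5). At 300 patients power is at least 99.9% either way, and only the interval changes, from 4.54 to between 4.57 and 3.82 points.

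This rests on the protocol's SD of 20 and 12-point difference, three covariate terms, and the assumed R² range. Confidence is medium because R² is unknown. The closed-form figures have been recalculated and agree; the simulations have not been repeated independently.

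**What to change.** State in section 6 that the primary analysis is a linear model of each patient's percentage of time at 70–180 mg/dL on randomised group, adjusted for pre-randomisation values of:

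1. glucose: the mean over the 24 hours before randomisation, otherwise the last earlier value, with imputation of the pooled mean over both groups if there is none;
2. history of diabetes (yes/no);
3. insulin infusion at randomisation (yes/no).

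Also state that:

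- a binary covariate is dropped if either level has fewer than 5 patients, counted over both groups pooled and checked on covariate data alone before outcomes are compared;
- no value measured after randomisation is used as a covariate;
- the result is the adjusted mean difference with its 95% CI, using HC2 standard errors and a t reference with residual degrees of freedom;
- the unadjusted difference is reported as a sensitivity analysis.

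Keep 88 as the minimum.

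**Cost.** SAP wording and two defined data fields (pre-randomisation glucose, infusion at randomisation) taken from records already listed in section 5.o. No extra patients or visits. If the covariates explain nothing, the loss of power is about 1.5 points at 88 patients, 0.7 at 120 and 0.4 at 150.
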